3.2 Sample Size

Sample sizes are determined to provide preliminary information on safety, clinical activity, PDn, and PK. **The study has 2 parts: enrolling approximately 8 DLT evaluable subjects in each opened dose-evaluation cohort, and then expanding the selected doses by enrolling approximately 30 more subjects. Before opening dose-expansion arms, it must be determined that there are not more than 2 dose-limiting toxicities in 8 DLT-evaluable subjects at the dose selected for Dose-expansion. With combined number of subjects in both dose evaluation and expansion components, 38 subjects will allow an approximately 86% probability to detect an occurrence of an adverse event (AE) with 5% incidence rate.**

Assuming beta (0.5, 0.5) prior distribution for the DLT rate, 95% credible intervals for the DLT rate and the posterior probability of DLT rate being larger than 0.33 for each toxicity scenario are provided in Table 2. For example, when 3 out of 8 subjects have DLTs, the posterior probability of the DLT rate being >0.33 is 0.62.

Table 2. 95% Credible Intervals for the Dose-limiting Toxicity Rate and Probabilities of Dose-limiting Toxicity Rate Being Larger Than 0.33

Cohort Size	# DLTs Observed	95% Credible interval for the DLT Rate	
8	0	0	0.26
8	1	0.01	0.45
8	2	0.06	0.59
8	3	0.12	0.71
8	4	0.20	0.80
8	5	0.29	0.88
8	6	0.41	0.94
8	7	0.55	0.99
8	8	0.74	1

After the safety evaluation of the first 4 DLT evaluable subjects in each opened Cohort, CSRC recommended enrollment of an additional 4 subjects for up to 8 dose-evaluable subjects in total. Upon the safety evaluation of the opened dose-evaluation cohorts, dose-expansion Arm 1 (KRd 70 mg/m² QW) for NDMM and Arm 2 (KRd 70 mg/m² QW) for RRMM were planned to enroll approximately 30 subjects each. However, among 9 NDMM subjects enrolled in Arm 1, 2 serious adverse events (SAE) were observed and the enrollment stopped. The CSRC determined to add a 2-step-up KRd regimen in Cohort 4 NDMM (KRd 56/70 mg/m² QW) in the Dose-evaluation component. Following the DLT rules above, the CSRC elected to open the second NDMM dose-expansion arm (Arm 3: KRd 56 mg/m² QW) where approximately 30 NDMM subjects (upon protocol amendment 3) were planned to be enrolled.

4. Covariates and Subgroups

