9.1 General Considerations

In general, the data will be presented in the CSR by considering RRMM patient groups (Cohort 1, Cohort 2 and Arm 2) and NDMM patient groups (Arm 1, Cohort 4 and Arm 3) separately. The data will be presented by each assigned dose cohort and by combined dose cohort in RRMM group and NDMM group. The dose cohort grouping is as follows.

RRMM patient groups:

1. RRMM 56 mg/m² (n=10) – Cohort 1
2. RRMM 70 mg/m² (n=12) – Cohort 2
3. RRMM 70 mg/m² (n=34) – Arm 2
4. RRMM 70 mg/m² (n = 46) – Cohort 2 + Arm 2

NDMM patient groups:

1. NDMM 70 mg/m² (n=9) – Arm 1
2. NDMM 56/70 mg/m² (n=9) – Cohort 4 (step up dosing)
3. NDMM 70 mg/m² (n=18) – Arm 1 + Cohort 4
4. NDMM 56 mg/m² (n=33) – Arm 3

Summary statistics will be provided for selected study variables. For continuous variables, the number of subjects with non-missing data (n), mean, standard deviation, median, minimum, and maximum will be presented. For discrete variables, the frequency and percentage distribution will be presented. Unless otherwise stated, the denominator for percentages is the number of subjects in the analysis set of interest for the summary. Graphical methods will be used, as appropriate, to illustrate study endpoints.

Confidence interval, when presented, will be constructed at the 95% level. For binomial variable, exact distribution methods will be employed. The distribution of time-to-event endpoints will be summarized by Kaplan-Meier method. Quartiles including median will be estimated by Kaplan-Meier along with their 95% confidence intervals.

Individual subject data recorded on the electronic case report forms (eCRFs) and any derived data will be presented in dataset tabulations.

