Appendix A. Dose Intensity Calculations

Dose intensity is calculated for each drug component and expressed as an average dose per unit of time. In this study, we choose the time unit to be week.

1. The formula for Actual Dose Intensity (mg/m²/wk or mg/wk) is defined as:

$$\text{Actual Dose Intensity (mg/m}^2\text{/wk or mg/wk)} = \frac{\text{Cumulative actual dose (mg or mg/m}^2\text{)}}{\text{Duration of exposure (wk)}}$$

- Cumulative actual dose (mg or mg/m²) received of carfilzomib and dexamethasone is defined as the cumulative dose of carfilzomib/dexamethasone, respectively, a subject received during the treatment period of the study.
- Duration of exposure (weeks) is defined as
$$\frac{(\text{last dose date} - \text{first dose date}) + \text{planned interval to next treatment week}}{7 \text{ days}}$$

Carfilzomib dosing schedule and planned interval

Cycle	Cycle Day of Treatment	Dose (mg/m ²)	Interval (Days) to Next Planned Treatment Week (or Completion)
1	Day 1	20	7
	Day 8	56 if Cohort 1; Cohort 4; Arm 3 70 if Cohort 2; Arm 1; Arm 2	7
	Day 15	56 if Cohort 1; Cohort 4; Arm 3 70 if Cohort 2; Arm 1; Arm 2	14
2 -18	Day 1	56 if Cohort 1; Arm 3 70 if Cohort 2; Cohort 4; Arm 1; Arm 2	7
	Day 8	56 if Cohort 1; Arm 3 70 if Cohort 2; Cohort 4; Arm 1; Arm 2	7
	Day 15	56 if Cohort 1; Arm 3 70 if Cohort 2; Cohort 4; Arm 1; Arm 2	14

Dexamethasone dosing schedule and planned interval

Cycle	Cycle Day of Treatment	Dose (mg)	Interval (Days) to Next Planned Treatment
1 - 8	Day 1	40	7
	Day 8	40	7
	Day 15	40	7
	Day 22	40	7
9 -18	Day 1	40	7
	Day 8	40	7
	Day 15	40	14

Lenalidomide dosing schedule and planned interval

Cycle	Cycle Day of Treatment	Dose (mg)	Interval (Days) to Next Planned Treatment
1 - 18	Day 1 - 7	25	7
	Day 8 – 14	25	7
	Day 15 - 21	25	7

2. The formula for Planned Dose Intensity (mg/m²/wk or mg/wk) is defined as:

$$\text{Planned Dose Intensity (mg/m}^2\text{/wk or mg/wk)} = \frac{\text{Cumulative planned dose (mg/m}^2\text{ or mg)}}{\text{Number of protocol specified treatment weeks}}$$

- Number of protocol specified treatment weeks is the sum of treatment weeks the patient completed. It is counted by 4 weeks for a completed or skipped cycle. For the last cycle, use the following rules to count:

Carfilzomib

1 week if the last dose is on Day 1;
2 weeks if the last dose is on Day 8;
4 weeks if the last dose is on Day 15;

Example: Patient's last carfilzomib is on cycle 2 Day 8. The number of protocol specified treatment weeks is D=4x1+2=6 weeks.

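### Does the 86% chance of seeing a 5% adverse event overstate what the newly diagnosed (NDMM) part of the study can detect after Amendment 3?

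*SAP*

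**What the plan says.** SAP 3.2 describes a two-part design: about 8 DLT-evaluable subjects in each opened dose-evaluation cohort, "and then expanding the selected doses by enrolling approximately 30 more subjects". It then gives the detection statement, which assumes a true incidence of 5%: "With combined number of subjects in both dose evaluation and expansion components, 38 subjects will allow an approximately 86% probability to detect an occurrence".

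The last paragraph of the same section recounts what happened in NDMM. Arm 1 stopped after 9 subjects. The Cohort Safety Review Committee (CSRC) decided to "add a 2-step-up KRd regimen in Cohort 4 NDMM (KRd 56/70 mg/m² QW"), and afterwards "the CSRC elected to open the second NDMM dose-expansion arm (Arm 3: KRd 56 mg/m² QW"), with about 30 subjects planned.

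SAP Appendix A gives the planned carfilzomib dose for Cycles 2–18 as "70 if Cohort 2; Cohort 4; Arm 1; Arm 2" and "56 if Cohort 1; Arm 3". SAP 9.1 lists "NDMM 70 mg/m² (n=18) – Arm 1 + Cohort 4" and "NDMM 56 mg/m² (n=33) – Arm 3" among the NDMM groups.

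Protocol 13.7 carries the same justification, worded as 38 RRMM and 38 NDMM subjects over the dose-finding and expansion components combined. The Protocol Synopsis (planned number of subjects) builds the NDMM 38 as about 8 in dose evaluation plus about 30 in the second NDMM expansion.

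**The concern.** Read straight through, SAP 3.2 suggests that 38 means 8 subjects on a dose plus 30 more on that same dose. For RRMM this is so, because Cohort 2 and Arm 2 share a regimen. For NDMM it is not: Cohort 4 steps up to 70 mg/m² from Cycle 2, while Arm 3 stays at 56 mg/m². Arm 3 thus has no NDMM dose-evaluation subjects on its own regimen to add to its 30. SAP 9.1 also lists no NDMM group of 38; it reports Arm 3 alone and combines Cohort 4 with Arm 1 instead.

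Safety is the primary objective. If 86% were a promise about the NDMM regimen carried into expansion, a reader would take too much reassurance from an event not being seen there.

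**Working it through.** **Formula.** P(at least one event) = 1 − (1 − p)^n, with p = 0.05 from SAP 3.2.

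**The plan's own figure.** n = 38: 1 − 0.95^38 = 1 − 0.1424 = 0.8576, which is the stated 86%.

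**Other groupings.** Enrolled numbers come from SAP Table 1 and SAP 9.1, planned numbers from SAP 3.2 and the Protocol Synopsis.

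| Group | n | 1 − 0.95^n |
|---|---|---|
| Arm 3, planned | 30 | 78.5% |
| Arm 3, enrolled | 33 | 81.6% |
| Cohort 4 + Arm 3, planned (NDMM, two regimens) | 8 + 30 = 38 | 85.8% |
| Cohort 4 + Arm 3, enrolled | 9 + 33 = 42 | 88.4% |
| All NDMM, enrolled | 9 + 9 + 33 = 51 | 92.7% |
| 20/70 regimen in RRMM, planned: Cohort 2 + Arm 2 | 8 + 30 = 38 | 85.8% |
| 20/70 regimen in RRMM, enrolled | 12 + 34 = 46 | 90.6% |
| 20/56 regimen, planned: Cohort 1 (RRMM) + Arm 3 (NDMM) | 8 + 30 = 38 | 85.8% |
| 20/56 regimen, enrolled | 10 + 33 = 43 | 89.0% |

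**Which group does the sentence speak about?** There are three possible readings.

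1. *By population.* This is how Protocol 13.7 puts it. The NDMM 38 is the Synopsis count of about 8 plus about 30. The statement is true as planned and conservative as enrolled (88.4%, or 92.7% with Arm 1 included).
2. *By regimen.* This is the reading that the SAP's remark about expanding selected doses invites. The 20/70 regimen has Cohort 2 and Arm 2. The 20/56 regimen was evaluated in Cohort 1 and expanded in Arm 3; footnote d to Protocol Figure 1 says that Arm 3 follows the Cohort 1 regimen. Both have about 38 planned and more than 38 enrolled. For 20/56 the two parts come from different disease populations, but the SAP sentence does not separate populations.
3. *By population and regimen together.* Only here does 38 fail for NDMM. Arm 3 falls short of 85.8% by 85.8 − 78.5 = about 7 points planned and 85.8 − 81.6 = about 4 points enrolled. Neither document makes this claim. The Synopsis ties a selected dose to the RRMM 38 only and names no regimen for the NDMM 38.

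**Is the NDMM population a reporting level?** Protocol 13 plans summaries by RRMM and NDMM population as well as by dose cohort. SAP Section 10 declares no departure from the protocol's analyses, and SAP 9.6.1 orders its adverse event tables by incidence in a total group. The lack of an all-NDMM line in SAP 9.1 is therefore weak evidence that 86% was meant for a single regimen.

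**The case for a change.** The best argument for the concern is one of timing and wording. The SAP change log shows that the sample size summary was added in October 2019, well after Protocol Amendment 3 of December 2016, in the same SAP amendment that updated the NDMM counts. The protocol's explicit split into 38 RRMM and 38 NDMM subjects became an undivided 38, placed close to the remark about expanding selected doses. SAP 9.1 presents RRMM and NDMM separately, so nobody will see a Cohort 1 + Arm 3 table. This is also the section's only statement about detecting adverse events in general, since its Table 2 covers DLTs only. A reader could carry 86% over to Arm 3, where the chance of missing a 5% event is 21.5% (planned) or 18.4% (enrolled) rather than 14.2%.

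The figures stand, as does the fact that no NDMM group on one regimen reaches 38. What does not follow is that SAP 3.2 is wrong. The change log describes the added text as a summary of the justification, and Protocol 13.7 is accurate for pooled NDMM subjects. A less specific summary of an accurate statement does not become inaccurate because a narrower meaning could be read into it. Nor is the reader left uninformed: the same section gives the regimens and the planned size of Arm 3, and Table 1 just before it gives the enrolled number in all six groups.

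**Conclusion.** The concern does not hold. The 86% is correct for the 38 subjects on which it is conditioned. That number fits the planned NDMM population and also each of the two expanded regimens, with 20/56 counted across RRMM and NDMM. The difference of about 7 points (planned) or 4 points (enrolled) appears only when the figure is applied to Arm 3 alone, which the plan does not do.

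Nothing depends on the figure. SAP 2.2 plans no formal hypothesis testing, the sample sizes are meant to give preliminary information, and no decision rule, analysis or enrolment number uses the 86%. The DLT credible intervals are a separate justification and are unaffected. Stating a probability for each reporting group would be a matter of presentation, not the repair of an error.

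This conclusion rests on taking the SAP sentence as a summary of Protocol 13.7, as the change log describes it, and on Arm 3 sharing the Cohort 1 regimen, as footnote d to Protocol Figure 1 states.

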4.1 Planned Covariates

Not Applicable.

4.2 Subgroups

No subgroup analyses are planned in this study.

5. Definitions

Baseline

The baseline value is the closest recorded measurement prior to the first dose of study drug. If there are multiple valid records on an individual at the same date, then the record closest to cycle 1 day 1 will be used.

Best overall response by computational assessment

Best overall response will be derived using the Onyx Response Computational Assessment (ORCA) for multiple myeloma disease assessments based on the International Myeloma Working Group Uniform Response Criteria (IMWG-URC) ([Durie et al. 2006](#), with revisions, [Rajkumar, et al. 2011](#)). The detailed algorithm is documented in a separate document.

Best overall response by investigator assessment

Best overall response by investigator assessment is the best confirmed response by the analysis trigger date based on the responses by visit collected on myeloma response assessment CRF. The following confirmatory assessments are required for all response categories (sCR, CR, VGPR and PR) and PD:

- All laboratory-based progressive disease and all responses require two consecutive assessments made at any time before initiation of any new therapy. Confirmatory lab samples should be separated by at least one calendar day.
- Progressive disease by non-laboratory-based assessment (ie, plasmacytoma or skeletal lesion) does not require confirmatory report.
- All response categories also require no evidence of progression including new bone lesion, if radiographic studies are performed.
- Confirmation of CR or sCR requires local pathology review of a bone marrow biopsy or aspirate (a repeat confirmatory bone marrow sample is not required)
- Extramedullary plasmacytoma evaluation is required to confirm PR, CR, or sCR (if present at baseline)

Best overall response will be decided in the following order of confirmed responses: sCR, CR, VGPR, PR, SD, PD starting from the best to the worst.

End of Study Date for a Subject

The end of study date is the date recorded on the End of Study page for an enrolled subject.

First Dose Date

The first dose date is the date on which a subject is administered the first dose of any study drug.

Fluorescent in Situ Hybridization (FISH) Risk Group

Subjects in this study had FISH analysis performed by a central study laboratory and local laboratory.

For central laboratory FISH: Subjects with chromosomal abnormalities (CA) t (4;14) or t (14;16) in $\geq 10\%$ of screened plasma cells, and/or deletion 17p in $\geq 20\%$ of screened plasma cells are in high risk group. Subjects with other CA or normal cytogenetics are in standard risk group.

For local laboratory FISH (captured on eCRF): Subjects with chromosomal abnormalities (CA) t (4; 14) or t (14;16) and/or deletion 17p detected on FISH are in high risk group. Subjects with other CA or normal cytogenetics are in standard risk group.

Investigational Product (IP)

IP for this study refers to Kyprolis® (carfilzomib).

Informed Consent Date

The informed consent date is the date on which a subject signs the informed consent for this study.

International Staging System (ISS) Stage at Baseline

ISS stage at baseline will be calculated using serum beta-2 microglobulin and serum albumin value collected at baseline based on the criteria published by the International Myeloma Working Group ([Greipp 2005](#)).

ISS Stage I: Serum beta-2 microglobulin < 3.5 mg/L and serum albumin ≥ 3.5 g/dL

ISS Stage II: Serum beta-2 microglobulin < 3.5 mg/L and serum albumin < 3.5 g/dL or serum beta-2 microglobulin $3.5- < 5.5$ mg/L irrespective of the serum albumin

ISS Stage III: Serum beta-2 microglobulin ≥ 5.5 mg/L

Revised International Staging System (R-ISS) Stage at Baseline

R-ISS stage at baseline will be calculated using ISS (serum beta-2 microglobulin and serum albumin value collected at baseline, with ISS calculated as above), cytogenetic

risk group by FISH (central lab data, local lab data), and LDH, based on the criteria published by the International Myeloma Working Group ([Palumbo, 2015](#)):

R-ISS Stage I: Serum beta-2 microglobulin < 3.5 mg/L, serum albumin \geq 3.5 g/dL and standard risk CA by FISH and normal LDH

R-ISS Stage II: Not R-ISS I or III

R-ISS Stage III: ISS III and either high risk CA by FISH or greater than normal LDH

Last Dose Date

The last dose date is the date on which a subject is administered the final dose of any study drug.

Refractory to prior multiple myeloma therapy

Subject is refractory to a drug received in prior regimens if the data collected on prior multiple myeloma therapy CRF indicates that any of the following criteria is met:

- a. Best Response to any regimen containing the drug is stable disease or progressive disease
- b. Reason the drug was stopped is progression in any regimen
- c. Date of relapse/progression is after start date and within 60 days after stop date of the drug in any regimen

Study Day 1

Study day 1 is the earliest date when carfilzomib, lenalidomide, or dexamethasone is given for subjects who receive at least one dose of study drug, enrollment date for subjects who are enrolled but not treated.

Study Day

The number of days from the study day 1 to a date of interest, inclusive: Study day = (date of interest – date of study day 1) + 1.

Unless otherwise specified, the timing of all study-related events, assessments, and interventions will be calculated relative to study day 1. Study day –1 will be the day before study day 1, and in general for assessments prior to study day 1, study day is defined as:

$$\text{Study Day } n = (\text{date of interest} - \text{date of Study day 1})$$

Subject Incidence Rate

The subject incidence rate for a given event is defined as the number of subjects with one or more reported occurrence of the event divided by the number of subjects who had the opportunity to experience the event.

Treatment-emergent Adverse Event

Treatment-emergent adverse events are **defined as any adverse events starting on or after the first dose of any study drug, and up to including 30 days after the last dose of any study drug or End of Study date, whichever is earlier.**

6. Analysis Sets

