7 SUBJECT SCREENING

A signed and dated informed consent form (ICF) will be obtained before any study-specific tests may be performed. Evaluations obtained as part of routine medical care and performed during the screening period may be used in place of the study-specific evaluations, provided they meet the time windows described below. It is recommended that study-specific tests unrelated to subject eligibility (including a bone marrow aspirate) be done only after screening tests confirm subject eligibility for the study. Subjects will acknowledge and agree to the possible use of this information for the study by giving informed consent.

All subjects who sign consent will be assigned a unique study number. This number will be used to identify the subject throughout the clinical study and must be used on all study documentation related to that subject.

The screening period for a particular subject commences at the point at which the subject signs the ICF, and must be completed within 21 days before dosing on Cycle 1 Day 1.

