10.1.3 PHYSICAL EXAMINATION

A physical examination will be performed during Screening, on Day 1 of Cycles 2 through 18, and at the EOT. Physical exam will include:

- ECOG PS
- Examination of cardiovascular and respiratory systems
- Weight
- BSA (at Screening and on Day 1 of Cycles 2–18 only)
- Height (at Screening only)

Abnormal physical examination findings during Screening will be captured as medical history. Abnormal physical examination findings observed after signing of the informed consent will be recorded as AEs.

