12 SAFETY DATA COLLECTION, RECORDING, AND REPORTING

12.1 DEFINITION OF SAFETY EVENTS

12.1.1 *ADVERSE EVENTS*

An AE is defined as any untoward medical occurrence in a clinical trial subject. The event does not necessarily have a causal relationship with study treatment. The investigator is responsible for ensuring that any AEs observed by the investigator or reported by the subject are recorded in the subject's medical record.

The definition of AEs includes worsening of a pre-existing medical condition. Worsening indicates that the pre-existing medical condition or underlying disease (eg, diabetes, migraine headaches, gout) has increased in severity, frequency, and/or duration more than would be

expected, and/or has an association with a significantly worse outcome than expected. A pre-existing condition that has not worsened more than anticipated (ie, more than usual fluctuation of disease) during the study or involves an intervention such as elective cosmetic surgery or a medical procedure while on study, is not considered an AE.

For situations when an AE or SAE is due to multiple myeloma, report all known signs and symptoms. Death due to disease progression in the absence of signs and symptoms should be reported as the primary tumor type (eg, multiple myeloma).

Note: The term “disease progression” should not be used to describe the disease-related event or AE.

The investigator’s clinical judgment is used to determine whether a subject is to be removed from treatment due to an AE. In the event a subject, or subject’s legally acceptable representative requests to withdraw from protocol-required therapies or the study due to an AE, refer to [Section 11](#) for additional instructions on the procedures recommended for safe withdrawal from protocol-required therapies or the study.

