12.2 SAFETY EVENT REPORTING PROCEDURES

12.2.1 ADVERSE EVENTS

12.2.1.1 Reporting Procedures for Adverse Events That do not Meet Serious Criteria

The investigator is responsible for ensuring that all AEs observed by the investigator or reported by the subject that occur after signing the informed consent form through 30 days after receiving the last dose of study drugs are reported using the Event CRF.

If initiation of new anticancer therapy occurs within 30 days following the last dose of study drugs, the date of new anticancer therapy will be recorded on the appropriate eCRF. In addition, the investigator should report any AEs that may occur after this time period which are assessed to have a reasonable possibility of being associated with study drug.

For subjects who complete the EOT visit less than 30 days following the last dose of study drug, a follow-up of ongoing AEs should be attempted by telephone and documented in the

subject's source file. AEs continuing at 30 days after the last dose of study treatment should have a comment in the source file by the investigator that the event has stabilized or is not expected to improve.

The investigator must assign the following AE attributes:

- AE diagnosis or syndrome(s), if known (if not known, signs or symptoms),
- Dates of onset and resolution (if resolved),
- Severity (and/or toxicity per protocol),
- Assessment of relatedness to carfilzomib and/or other protocol-required therapies
- Action taken.

The adverse event grading scale used will be the Common Terminology Criteria for Adverse Events (CTCAE). The grading scale used in this study is described in [Appendix F](#).

The investigator must assess whether the AE is possibly related to carfilzomib and/or other protocol-required therapies. This relationship is indicated by a “yes” or “no” response to the question: Is there a reasonable possibility that the event may have been caused by carfilzomib and/or other protocol-required therapies?

In the event of a possible drug-related AE, the investigator should to the best of his/her ability assess its relationship to each of the study drugs: carfilzomib, lenalidomide, and/or dexamethasone.

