9.6.1 Adverse Events and Disease-related Events

The Medical Dictionary for Regulatory Activities (MedDRA) version 21.0 or later will be used to code all adverse events (AEs) to a system organ class (SOC) and a preferred term (PT). The severity of AEs will be coded according to NCI-CTCAE v 4.03.

Treatment emergent adverse events will be summarized based on the number (%) of subjects experiencing events by MedDRA SOC and PT. The denominator for the percentage will be based on the number of subjects in the Safety Analysis Set.

Summaries of the subject incidence of the following TEAEs will be provided by SOC and/ or PT:

- All TEAEs
- TEAEs grade 3 or higher
- Fatal TEAEs
- Serious TEAEs
- TEAEs leading to withdrawal of carfilzomib
- Treatment-related TEAEs
- Treatment-related TEAEs grade 3 or higher
- **Treatment-related fatal TEAEs**
- **Treatment-related serious TEAEs**
- **Treatment-related TEAEs leading to withdrawal of carfilzomib**

Summaries that are displayed by SOC and PTs will be ordered by descending order of incidence of SOC and PT within each SOC for the total group. Summaries of TEAEs, and SAEs will be tabulated by SOC, PT and grade. Summaries of TEAEs, treatment-related AEs, and SAEs will also be provided by descending order of incidence of PTs in the total group

All TEAEs will be included in listings by subject. Listings of AEs determined to be DLTs, SAEs, AEs leading to discontinuation of study and AEs leading to discontinuation of investigational product will be provided.

A summary of the number of deaths and the cause of death, classified by deaths within 30 days of last dose of study drug and deaths more than 30 days after the last dose, will be provided.

Subject incidence of adverse events of interest (standardized MedDRA queries (**SMQ**) and/or Amgen MedDRA queries (**AMQ**)) will also be summarized according to their categories, PTs and grade. The adverse events of interest would include

- Acute renal failure (SMQ Narrow search)
- Cardiac arrhythmias (SMQ Narrow search)
- Cardiac failure (SMQ Narrow search)
- **Cardiomyopathy (SMQ Narrow search)**

- Dyspnoeas (HLT) - MedDRA Search Strategy HLT
- Embolic and thrombotic events, venous (SMQ Narrow search)
- Haematopoietic erythropenia (SMQ Broad search)
- Haematopoietic leukopenia (SMQ Narrow search)
- Haematopoietic thrombocytopenia (SMQ Narrow search)
- Haemorrhage terms (excl laboratory terms) (SMQ Narrow search)

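### SAP section 5 defines a TEAE by start date alone, so a screening-onset AE that worsens to Grade 3+ on KRd can be left out of the TEAE tables and the by-subject AE listing

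*SAP*

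**What the plan says.** **The rule.** SAP section 5 (Definitions) treats as treatment-emergent "any adverse events starting on or after the first dose of any study drug". The window closes 30 days after the last dose of any study drug or at the end-of-study date, whichever is earlier. Start date is the only criterion; grade and seriousness play no part.

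**When AEs are collected.** Under Protocol 12.2.1.1, AEs that "occur after signing the informed consent form through 30 days after receiving the last dose of study drugs are reported using the Event CRF". Protocol section 7 starts screening at the signing of consent and says that it "must be completed within 21 days before dosing on Cycle 1 Day 1". AEs with a pre-dose onset can therefore be in the database.

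**How worsening is handled.** Protocol 12.1.1 says: "The definition of AEs includes worsening of a pre-existing medical condition". It applies this only where the worsening exceeds what would be expected. Protocol 12.2.1.1 lists onset and resolution dates and severity among the attributes of an AE. It does not say whether a change of grade in an open AE starts a new record.

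**Examination findings.** Protocol 10.1.3 says: "Abnormal physical examination findings observed after signing of the informed consent will be recorded as AEs". The sentence before it sends findings made during screening to medical history, although screening begins at consent.

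**What is reported.** SAP 9.6.1 names ten subject-incidence tables, all of TEAEs, and adds: "All TEAEs will be included in listings by subject". The same section also plans tables and listings worded as SAEs, treatment-related AEs or adverse events of interest, without the TEAE limit.

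**The concern.** Safety and tolerability is the primary endpoint (Protocol 13.1.1, SAP 2.1), measured by type, incidence and severity of AEs. An event that was mild at first dose and becomes Grade 3 on KRd is treatment-period toxicity. Under a start-date rule it belongs to the pre-treatment period if the site keeps it on the record opened in screening. Any such omission lowers reported incidence and never raises it. The dose groups are small, so a single subject can visibly change a row.

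The rule also sits oddly beside SAP 8.3. When the start month or year matches that of the first dose and the event could have been present on treatment, Table 3 imputes the first-dose date, which makes the event a TEAE. A screening AE with an unknown start day can thus be counted without any worsening, while a fully dated one that demonstrably worsened is not.

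**Working it through.** **1. The plan's own AE figure.** Protocol 13.7 and SAP 3.2 give about 86% probability of seeing at least one AE of 5% incidence in 38 subjects. 1 − 0.95^38 = 0.858, so the figure reproduces. The point does not depend on it.

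**2. Trace one event.** Suppose an AE starts in screening at Grade 1 or 2, is still open at first dose, and rises to Grade 3 in Cycle 2.
- If the worsening is a new record, its start date is in Cycle 2, so it is a TEAE and nothing is lost.
- If the grade is updated on the existing record, the start date precedes the first dose, so it is not a TEAE.

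Neither document chooses between the two.

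**3. Follow the second branch through SAP 9.6.**

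| Output | Limited to TEAEs as worded? | Non-serious Grade 3+ case | Serious or fatal case |
|---|---|---|---|
| Ten incidence tables: all, Grade 3+, fatal, serious, leading to carfilzomib withdrawal, and their treatment-related versions | Yes | Missed | Missed |
| TEAEs by SOC, PT and grade; TEAEs by PT | Yes | Missed | Missed |
| General by-subject listing | Yes | Missed | Missed |
| SAEs by SOC, PT and grade; SAEs by PT; SAE listing | No | Does not apply | Shown |
| Treatment-related AEs by PT | No | Shown if related; no grade named | Shown if related |
| Events of interest by category, PT and grade | No | Shown if within a listed search | Shown if within a listed search |
| Listings of DLTs and of AEs leading to discontinuation | No | Shown only if the event qualifies | Shown only if the event qualifies |
| Deaths and causes | No | Does not apply | Fatal case shown |
| Laboratory grade shifts (SAP 9.6.2) | Independent of AE records | Graded laboratory values only | Graded laboratory values only |

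The non-serious clinical event outside the events of interest has the least cover. A fatal case would appear among deaths but not among fatal TEAEs, and a serious case among SAEs but not among serious TEAEs.

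**4. Size of one omission.** Group sizes are from SAP Table 1 and SAP 9.1; the effect on a row is at most 1/n.
- Arm 1 or Cohort 4: 1/9 = 11.1 percentage points
- Cohort 1: 1/10 = 10.0
- Cohort 2: 1/12 = 8.3
- Arm 3: 1/33 = 3.0
- Arm 2: 1/34 = 2.9
- Arm 1 + Cohort 4: 1/18 = 5.6
- Cohort 2 + Arm 2: 1/46 = 2.2

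SAP section 5 counts a subject once per event. The all-TEAE or overall Grade 3+ row therefore changes only if the subject has no other qualifying TEAE.

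**5. Illustration on an assumption.** The documents do not give the share f of events lost in this way. With incidence 0.05(1 − f) and n = 38, the detection probability of 0.858 becomes 0.843, 0.826, 0.788 or 0.742 for f = 5%, 10%, 20% or 30%. This shows sensitivity and predicts nothing.

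**The case against.** The strongest reply is that the loss rests on a recording convention that cannot be seen. Protocol 14.5 leaves CRF instructions to completion guidelines and other study documents, and the SAP change log ties the current TEAE wording to a sponsor standard that is not supplied. If sites enter a grade increase as a new AE, the start-date rule loses nothing. This stands: the omission is possible, not established. It is also a reason to write the convention down.

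A reader might infer that a worsening screening AE enters no AE table at all, even when serious or fatal. The documents do not support that. SAP 9.6.1 words several outputs without the TEAE limit, and serious and fatal cases fall within them. Typical candidates such as hypertension, dyspnea, peripheral neuropathy and respiratory tract infection are listed events of interest, so a downward bias in those tables is not shown either. Two doubts remain. SAP 9.6.1 uses both serious TEAEs and SAEs without saying whether they differ, and the unqualified tables might be programmed as TEAE-only. The SAE listing and death summary would still remain.

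The examination-findings rule in Protocol 10.1.3 also narrows the gap. A finding placed in medical history that later worsens beyond expectation is an AE under Protocol 12.1.1, with an on-treatment onset, and so a TEAE. This does not help an AE already open on the Event CRF.

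**Conclusion.** The concern holds in limited form. The TEAE definition has no worsening clause, and a screening-onset AE kept as one record can be left out of the ten listed TEAE tables and the by-subject listing after it reaches Grade 3 or higher on treatment. The real exposure is non-serious clinical events that are not events of interest. For serious and fatal events the problem is outputs that would not reconcile, not disappearance.

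The conclusion assumes that at least some sites update an open record instead of starting a new one, and that the tables are programmed as worded. How many subjects are affected cannot be derived from the documents, so the 1/n figures are upper limits per subject and per row, not an estimate of bias. The point deserves correction because it touches the primary endpoint and the remedy is cheap. It does not show that the overall safety profile would be misreported.

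**What to change.** 1. Extend the SAP section 5 definition along these lines: *An AE with onset before the first dose of any study drug is also treatment-emergent if its CTCAE grade rises or it becomes serious on or after the first dose and within the existing TEAE window.* Alternatively, state in the SAP and the CRF guidance that such worsening is entered as a new AE with its own onset date.
2. State in SAP 9.6.1 whether the tables of SAEs, treatment-related AEs and adverse events of interest are limited to treatment-emergent events, so that they reconcile with the TEAE tables.
3. Where the date of worsening cannot be established, flag the event in the listing and do not count it. Counting every pre-dose-onset Grade 3+ or serious AE still open at first dose would label events that peaked before dosing as treatment-emergent. In a group of 9 that is the same 11.1 points in the other direction.

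The cost is one clause, one derived flag and slightly higher reported incidence.
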